5.2.6 Number of Hours Subjects are Pain Free (NRS ≤ 2)

The number of hours subjects are pain free (from 0-72 hours) will be derived as follows:

A horizontal line will be drawn at NRS of 2 on a line plot of a subject's NRS pain intensity scores. Then the time between the hours of 0 and 72, inclusive, where NRS pain intensity score is less or equal to 2 will be summed; linear interpolation will be used to calculate the amount of time for when the line plot and horizontal line intersects. If a subject took rescue medication, the next 4 hours after taking any rescue medication will not be considered pain

free even if the NRS pain intensity score is ≤ 2 . Subjects that drop out will not have the time after they drop out considered to be ≤ 2 following their last reported NRS.

5.2.7 Proportion of Subjects Who Are Opioid Free

The proportion of subjects who are opioid free 0-<24, 0-<48 and 0-<72 hours and 24-<48 hours and 48-72 hours will be derived as the number of subject who did not take opioids divided by the number of subjects per treatment group. Likewise, the proportion of subjects that are opioid free starting at 0, 12, 24, 36 hours will be reported. Subjects that drop out of the study prior to a given time point will be assumed to have not subsequently taken opioids, unless concomitant medication or diary data suggest that an opioid was available to them at that time (whether or not the subject reported taking it in the period in question).

5.2.8 Global Evaluation of Study Drug (GESD)

The global evaluation of study drug is assessed just before receiving the first dose of rescue medication and at the end of 24 hours, 48 hours, and 72 hours relative to time 0. This will be considered three ways:

- With all values reported as recorded
- With values following rescue censored
- With the pre-rescue values grouped with the subsequent time point and values following rescue censored

For the GESD, subjects will be asked to provide a graded response (4=excellent, 3=very good, 2=good, 1=fair, or 0=poor) to the statement “How would you rate the study drug you received to delay or reduce your foot pain?”

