2.2.2 Secondary Endpoints

The secondary endpoints are:

- Mean AUC of the NRS of pain intensity scores from time 0 through 48 and 72 hours (AUC₀₋₄₈; AUC₀₋₇₂) for ACP-044
- Mean AUC of the NRS of pain intensity scores from time 0 through 4, 6, and 12 hours (AUC₀₋₄; AUC₀₋₆; AUC₀₋₁₂), 24-48 hours (AUC₂₄₋₄₈), and 48-72 hours (AUC₄₈₋₇₂) for ACP-044
- Amount of rescue medication taken during 0-24, 24-48, and 48-72 hours (individually), 0-48 hours, and 0-72 hours

Study: ACP-044-004 Clinical Study Protocol Amendment 5

• Proportion of subjects who did not use rescue medication through 24, 48, and 72 hours

- Proportion of subjects who are pain free (NRS \leq 2) at 24, 48, and 72 hours
- Number of hours subjects are pain free (NRS \leq 2)
- Proportion of subjects who were opioid free during 24-48 hours and 48-72 hours
- Global evaluation of study drug just before time of first rescue medication and at the end of 24, 48, and 72 hours relative to time 0 (when first dose on Day 1 is administered)

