6.4.2 Global Evaluation of Study Drug

For the global evaluation of study drug subjects will be asked to provide a graded response (4=excellent, 3=very good, 2=good, 1=fair, or 0=poor) to the statement "How would you rate the study drug you received to delay or reduce your foot pain?" The time at which the statement is completed will be recorded.

Evaluation of study drug will be completed just before receiving the first dose of rescue medication, and at the end of 24 hours, 48 hours, and 72 hours relative to time 0 (when the first dose on Day 1 is administered). The evaluation of study drug should be performed before blood sample collection, ECG, and other procedures.

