12.1 Efficacy Variables

Primary Efficacy Endpoint

- The mean AUC_{0-24} of NRS of pain intensity scores (using 4 hour window for rescue medications)

Key Secondary Efficacy Endpoints

- Time to first rescue medication use after time 0 (when the first dose on Day 1 is administered)
- Proportion of subjects who were opioid free through 24 hours
- Proportion of subjects who were opioid free through 48 hours
- Proportion of subjects who were opioid free through 72 hours

Secondary Efficacy Endpoints

- The mean AUC_{0-48} of NRS of pain intensity scores (using 4 hour window for rescue medications)
- The mean AUC_{0-72} of NRS of pain intensity scores (using 4 hour window for rescue medications)
- The mean AUC_{0-4} of NRS of pain intensity scores (using 4 hour window for rescue medications)
- The mean AUC_{0-6} of NRS of pain intensity scores (using 4 hour window for rescue medications)
- The mean AUC_{0-12} of NRS of pain intensity scores (using 4 hour window for rescue medications)
- The mean AUC_{24-48} of NRS of pain intensity scores (using 4 hour window for rescue medications)

- The mean AUC_{48-72} of NRS of pain intensity scores (using 4 hour window for rescue medications)
- Amount of rescue medication taken during 0-24, 24-48, and 48-72 hours (individually), 0-48 hours, and 0-72 hours
- Proportion of subjects who did not use rescue medication through 24, 48, and 72 hours
- Proportion of subjects who are pain free (NRS ≤ 2) at 24, 48, and 72 hours
- Number of hours subjects are pain free (NRS ≤ 2)
- Proportion of subjects who were opioid free during 24-48 hours and 48-72 hours
- Global evaluation of study drug just before time of first rescue and at the end of 24, 48, and 72 hours relative to the time 0 (when the first dose on Day 1 is administered)

Exploratory Efficacy Endpoints

- Proportion of subjects with severe pain (defined as an NRS pain intensity score ≥ 7 at any timepoint through 72 hours)
- Foot and Ankle Ability Measure (FAAM)

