The proportion of subjects who are opioid free (did not take acetaminophen-hydrocodone oral tablet as rescue medication or any other opioid) through 24, 48, and 72 hours and during 0-<24 hours, 24-<48 hours, and 48-72 hours will be analyzed using a stratified CMH test controlling for site.

The risk difference, 95% confidence interval and p-values will be provided by treatment group pairwise.

Proportion of subjects who are pain free (NRS <2) at 24, 48, and 72 hours

The proportion of subjects who are pain free at 24, 48, and 72 hours will be analyzed using a stratified CMH test controlling for site.

The risk difference, 95% confidence interval and p-values will be provided by treatment group pairwise.

Number of hours subjects are pain free (NRS <2)

The number of hours subjects are pain free will be analyzed using ANOVA with treatment group and site as factors in the model. Each active dose group will be compared to placebo using this model.

The LS mean (SE), 95% confidence intervals, and p-values will be presented by treatment group. The LS mean difference (SE), associated 95% confidence intervals, p-values, and Cohen's d will be presented by treatment group pairwise.

Global evaluation of study drug just before time of first rescue and at the end of 24, 48, and 72 hours

The global evaluation of study drug (GESD) will be summarized as a categorical and as a continuous variable for each visit and for each censoring approach:

- With all values reported as recorded
- With values following rescue censored
- With the pre-rescue values grouped with the subsequent time point and values following rescue censored

The GESD will be analyzed by visit using ANOVA with treatment group and site as factors in the model.

The LS mean (SE), 95% confidence intervals, and p-values will be presented by treatment group. The LS mean difference (SE), associated 95% confidence intervals, p-values, and Cohen's d will be presented by treatment group pairwise.

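### The GESD rating taken just before first rescue exists only for subjects who take rescue, so an ANOVA of that time point is not a randomised comparison and would probably understate an effective drug's benefit

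*SAP*

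**What the plan says.** Protocol 6.4.2 ties the first GESD rating to a rescue dose: "Evaluation of study drug will be completed just before receiving the first dose of rescue medication". Further ratings follow at 24, 48 and 72 h. SAP 5.2.8 has the same schedule: "The global evaluation of study drug is assessed just before receiving the first dose of rescue medication". The scale runs from 0 (poor) to 4 (excellent).

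Both documents put the pre-rescue rating inside a secondary endpoint. Protocol 2.2.2 lists "Global evaluation of study drug just before time of first rescue medication and at the end of 24, 48, and 72 hours" and SAP 12.1 lists "Global evaluation of study drug just before time of first rescue and at the end of 24, 48, and 72 hours". The GESD sub-heading in SAP 13.3 repeats this, and the text below it says: "The GESD will be analyzed by visit using ANOVA with treatment group and site as factors in the model". LS mean differences, confidence intervals, p-values and Cohen's d follow for each pair of arms.

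SAP 5.2.8 and 13.3 ask for this under three handlings:

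- Handling 1: "With all values reported as recorded".
- Handling 2: "With values following rescue censored".
- Handling 3: "With the pre-rescue values grouped with the subsequent time point and values following rescue censored".

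Neither document says how a never-rescued subject is scored at the pre-rescue time point, gives a missing-data rule for the GESD, or says which handling is the main one.

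**The concern.** The plan expects some subjects never to take rescue. The proportion without rescue through 24, 48 and 72 h is itself a secondary endpoint (SAP 5.2.4 and 12.1), and the time-to-rescue analysis censors such subjects at 72 h (SAP 13.2). These subjects have the best rescue outcome, and they have no pre-rescue GESD.

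Rescue happens after randomisation, and treatment is meant to reduce it. A comparison of pre-rescue ratings therefore sets the placebo subjects who needed rescue against the active subjects who needed it despite treatment. If the drug spares rescue, the second group is the more strongly selected, and some of those the drug helped most are missing from it. The groups compared are not the randomised groups. Nor are they the Full Analysis Set, on which SAP 13.3 says secondary analyses are run. At stake is a reported p-value that could suggest subjects rate the drug no better than placebo when they do.

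**Working it through.** **1. What each handling does with a never-rescued subject.**

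- Handlings 1 and 2, pre-rescue time point: no value exists, so the row holds rescuers only.
- Handling 1 at 24, 48 and 72 h: all recorded ratings are used, from rescued and never-rescued subjects alike.
- Handling 2 at 24, 48 and 72 h: never-rescued subjects stay in and subjects already rescued drop out.
- Handling 3 at 24 h: a subject rescued by 24 h contributes the pre-rescue rating and anyone else the 24 h rating, so every rated subject is included.
- Handling 3 at 48 and 72 h: never-rescued subjects stay in and earlier rescuers drop out.

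Never-rescued subjects are thus lost only from the stand-alone pre-rescue row under handlings 1 and 2.

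**2. The plan's own figure.** SAP 3.5 assumes a difference of 23 and an SD of 50 on AUC0-24, with two-sided alpha 0.05. The normal approximation gives n = 2 × (1.960 + 0.842)² × (50/23)² = 74.2, so 75 per arm. The t-test power at 76 per arm is 80.4%, and 76/0.95 = 80. The stated 76, 80% and 80 reproduce. They concern the primary endpoint only; the plan gives no effect size for the GESD and no rescue rate.

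**3. Effect of restricting to rescuers.** Assumptions: latent pain is normal with SD 1; the drug lowers it by d = 23/50 = 0.46 SD in everyone (borrowed from the primary endpoint); the rating falls one for one with pain; rescue is taken when pain exceeds c. With λ(a) = φ(a)/(1 − Φ(a)), mean pain among rescuers is λ(c) on placebo and λ(c + d) − d on active. The rescuers-only difference is

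d − [λ(c + d) − λ(c)].

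At 50% placebo rescue, c = 0: 0.46 − (1.112 − 0.798) = 0.146. At 90%, c = −1.282: 0.46 − (0.358 − 0.195) = 0.297. The range is:

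| Rescued, placebo / active | Rated of 80, placebo / active | Difference among rescuers (SD) | Share of 0.46 kept |
|---|---|---|---|
| 30% / 16% | 24 / 13 | 0.11 | 23% |
| 50% / 32% | 40 / 26 | 0.15 | 32% |
| 70% / 53% | 56 / 42 | 0.20 | 43% |
| 90% / 79% | 72 / 64 | 0.30 | 64% |
| 95% / 88% | 76 / 71 | 0.34 | 75% |
| 99% / 97% | 79 / 78 | 0.42 | 90% |

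**4. Other patterns of response.** A simulation on the 0–4 scale (2,000,000 subjects per arm) used four assumed drug effects: a uniform shift, random responders, responders mainly among those with milder pain, and responders mainly among those with severe pain. Each was run at placebo rescue rates of 50, 70, 90 and 97%.

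- The rescuers-only difference was smaller than the all-subject difference in all 16 scenarios. It changed sign in two (−0.07 and −0.08 points against +0.33), both with response concentrated in milder pain.
- Handling 3 at 24 h equalled the all-subject difference, 0.33 to 0.42 points. This follows from the set-up, in which each subject has one rating and nobody drops out.
- Handling 3 at 48 and 72 h ranged from 0.08 to 0.50 points, because earlier rescuers are removed.

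**The case against.** The strongest reply is that the SAP already contains the repair. Handling 3 keeps never-rescued subjects at every scheduled time point and at 24 h includes every rated subject; handling 1 also keeps all recorded scheduled ratings. A reader might infer that the GESD endpoint as a whole leaves out never-rescued subjects. The documents do not support that. This part of the reply stands, but the SAP does not make handling 3 the main analysis, and the pre-rescue row under handlings 1 and 2 remains uncorrected.

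Second, a separate pre-rescue test is not explicit. The GESD is analysed by visit, and SAP Tables 2 and 3 contain no pre-rescue visit. That is fair, but Table 3 has no GESD row at all, so its silence settles nothing, while the sub-heading in SAP 13.3 names the time point. Either the test is run, with the selection problem, or a named part of the endpoint has no stand-alone analysis. Both call for clarification.

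Third, rescue could be nearly universal. Protocol 1.1 expects moderate to severe pain, time 0 follows discontinuation of the nerve block, and any ibuprofen dose counts as rescue (SAP 5.2.1). At 99% and 97% rescue, 90% of the difference survives. This stands, which is why the size is given as a range.

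Fourth, rescue sparing is tested in its own right through time to first rescue and the proportion without rescue. That also stands and limits the damage.

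**Conclusion.** The point holds for one row. Under handlings 1 and 2, an ANOVA of the pre-rescue GESD conditions on a post-randomisation outcome, omits never-rescued subjects and is not a randomised comparison. That follows from the documents alone, provided the implied test is run.

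Direction and size rest on assumptions. Attenuation is probable and appeared in every scenario tried. With an assumed true difference of 0.46 SD, roughly two thirds is lost at 50/32% rescue and about 10% at 99/97%. A reader might go further and infer a fixed bias, or a reversed effect. The documents give no rescue rate and no pattern of response that would support either; reversal needed response concentrated in subjects with milder pain.

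The GESD lies outside the fixed sequence in SAP 12.3. The primary endpoint, type I error control and sample size are unaffected.

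**What to change.** In SAP 5.2.8 and 13.3, before database lock:

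- Name handling 3 at 24 h as the main between-group GESD analysis in the Full Analysis Set: the pre-rescue rating if rescued by 24 h, otherwise the 24 h rating.
- Report the stand-alone pre-rescue rating descriptively, with the number rated per arm, no p-value, and a note that it covers rescued subjects only.
- Optionally add, as supportive, the rating at first rescue or at 72 h, whichever comes first. This needs a rule for subjects who discontinue before 72 h without rescue. It also needs a note that it mixes early and day-3 ratings in proportions that may differ by arm, which is why it should not be the main analysis.

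The cost is a few lines of SAP text and, if the supportive analysis is added, one derived variable. All ratings are already collected. The small downside is that one row loses its p-value.

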5.2.9 Proportion of Subjects with Severe Pain

The proportion of subjects with severe pain will be derived as the number of subjects with an NRS pain intensity score of ≥ 7 at any timepoint through 72 hours divided by the number of subjects per treatment group.

5.2.10 Foot and Ankle Ability Measure (FAAM)

The foot and ankle ability measure (FAAM) is assessed at Baseline and in the Safety Follow-up Period, 7 days after EOT/ET.

There are two subscales: activities of daily living (ADL) and Sports. For ADL subscale, there are 21 movements the subject rates as “4=no difficulty at all”, “3=slight difficulty”, “2=moderate difficulty”, “1=extreme difficulty”, “0=unable to do”, and “N/A”, and an overall grade for the level of function during usual activities of daily living, graded on a scale

of 0 to 100 with 100 being at the level of function prior to the foot and ankle problem and 0 being the inability to perform any of their usual daily activities.

For Sports subscale, there are 8 movements and an overall grade for the level of function during sports related activities, graded in the same manner as ADL (0-4 for items, 0-100 for overall grade).

Missing FAAM data will not be imputed.

Within subscale, the item score total will be derived as the sum of items with a response (NA responses are not counted). The total number of items with a response is multiplied by 4 to get the highest potential score (For ADL, if all 21 items have a response that has a score of 0-4, the highest potential score is 84, if there is one item with a NA or missing response, then the highest potential score is 80; the highest potential score for Sports subscale is derived similarly; however, the Sports subscale only has 8 items). The item score total will be divided by the highest potential score; this value will be multiplied by 100 to get a percentage. A higher percentage represents a higher level of physical function.

If there are less than 90% completed items (NA responses are considered as not completed), i.e., less than 19 items completed for ADL or less than 7 items for Sports subscales, then the corresponding item percentage score will be considered missing.

Total score will be derived as the sum of the ADL and Sports subscales. If either subscale is missing, total score will also be missing.

5.2.11 Columbia-Suicide Severity Rating Scale (C-SSRS)

The C-SSRS is assessed at Screening, Day -1 and Day 4 (EOT/ET).

The C-SSRS baseline/screening version will be administered at screening.

The C-SSRS version assessing information since the last visit will be completed at Day -1 and Day 4 (EOT/ET) visits.

There are 5 questions about suicidal ideation, representing 5 types of suicidal ideation: wish to be dead; non-specific active suicidal thoughts; active suicidal ideation with any methods (not plan) without intent to act; active suicidal ideation with some intent to act, without specific plan; active suicidal ideation with specific plan and intent. If a subject answers “yes” to any of these 5 questions, this subject will be counted as having suicidal ideation.

There are 5 questions about suicidal behavior, representing 5 types of suicidal behavior: preparatory acts or behavior; aborted attempt; interrupted attempt; actual attempt; suicide. If a subject answers “yes” to any of these 5 questions, this subject will be counted as having suicidal behavior.

Suicidality is defined as a subject who reported at least 1 occurrence of suicidal ideation or at least 1 occurrence of suicidal behavior at any post-Baseline visit including unscheduled and out of window visits.

Missing C-SSRS item scores will not be imputed.

5.3 Study Analysis Day

If the date of assessment occurs on or after the first dose date, then the study analysis day will be calculated as (date of assessment – first dose date) + 1. If the date of assessment occurs prior to the first dose date, then study analysis day will be calculated as (date of assessment – first dose post operation). There is no study analysis day 0.

5.4 Baseline Definition

In general, baseline for safety data and FAAM are defined as data collected which are prior to the administration of the first dose. If there is more than one value on or prior to first dose, the value closest to and prior to the receipt of the first dose, whether scheduled or unscheduled, will be used as the Baseline value.

NRS pain severity score does not have a baseline.

5.5 Analysis Visit Windows

Efficacy, safety, and PK assessments will be summarized by analysis visit and timepoint as presented in Table 2 and Table 3 below.

Study analysis visit window will be used to map visits using study day intervals. In Table 2, the first day of double-blind dosing is defined as “Study Analysis Day 1”.

Table 2 Analysis Visit Windows

Analysis Visit Name	Target Study Analysis Day	Study Analysis Day Interval
Baseline ^[1] (Day -1)	1	≤ 1 and pre-dose
Day 1	2	2
Day 2	3	3
Day 3	4	4
Day 4	5	5

[1] The Baseline is not applicable to NRS assessment.

Table 3 Analysis Timepoint Windows

Parameter	Target Study Timepoints	Timepoint Window
Vital Signs	Day -1 predose, Day 1: 2h, 4h, 6h postdose and then every 6 hours thereafter up to Day 4/EOT(12h, 18h, 24h, 30h, 36h, 42h, 48h, 54h, 60h, 66h, 72h...)	Predose assessment must be prior to dose on Day -1. For postdose records, the scheduled time will be used for analysis; the midpoint between each timepoint will be used to map the assessments such that there is no gap in windowing.
ECG	Day -1 predose, Days 1-3 at 1h postdose, and EOT/ET.	Predose assessments must be prior to dose on Day -1. For post-dose assessments, the midpoint between each timepoint will be used to map the assessments such that there is no gap in windowing.
PK Blood Samples	Day -1 predose within one hour of dosing, Day 1 between 2-3h postdose, Day 1 between 4-6h postdose, Day 2 predose, Day 3 between 2-6h postdose, Day 3 between 8-12h postdose, and in the event of an SAE or AE leading to discontinuation (if possible).	For time points prior to Day 2 predose, the window will be ± 15 min on top of the collection window range. For timepoints on Day 2 and beyond will be ± 1 hour on top of the collection window range.
Block Quality Assessments	Postoperatively, assessments will be performed and recorded hourly (± 15 minutes) at the top of each hour until 2200 hours. Between the hours of 2200 and 0600 hours, assessments will continue to be performed hourly (± 15 minutes) if subject is awake, but, even if asleep, the subject will be awakened to perform a Block Quality Assessment at 0300 hours (± 15 minutes). Block Quality Assessments will continue until the block is removed.	For each hour 0-24 post surgery completion, the time of the surgery completion defines analysis timepoint 0, a ± 30 min window will be used. For time 0 the window will start at the time of surgery completion.
NRS	Day 1: 0h (Time 0), 1h, 2h, 3h, 4h, 5h, 6h, 7h, 8h, 9h, 10h, 11h, 12, 15h, 18h, 21h, 24h, 30h, 36h, 42h, 48h, 54h, 60h, 66h, 72h, and then once daily in starting the morning of Day 4 until the follow-up clinic visit.	For each timepoint up to 72h the window will be ± 30 min. For AUC calculation, all NRS timepoints will be considered. Only windowed assessments will be summarized in the by timepoint summary and for specific steps outlined for the multiple imputation of missing data in the sensitivity analysis.

